**CONFIDENTIAL**

056-F275 Rev G Clinical Investigation Plan Template

# Enable Hernia Repair Clinical Investigation Plan

MDT21022

Version 5.0

Page 107 of 116

Medtronic

2. My abdominal wall causes me physical pain	

1. Strongly Disagree

2. Moderately disagree

3. Slightly disagree

4. Slightly agree

5. Moderately agree

6. Strongly agree

3. My abdominal wall interferes when I perform strenuous activities (e.g. heavy lifting)	

1. Strongly Disagree

2. Moderately disagree

3. Slightly disagree

4. Slightly agree

5. Moderately agree

6. Strongly agree

4. My abdominal wall interferes when I perform moderate activities (e.g. bowling, bending over)	

1. Strongly Disagree

2. Moderately disagree

3. Slightly disagree

4. Slightly agree

5. Moderately agree

6. Strongly agree

5. My abdominal wall interferes when I walk or climb stairs	

1. Strongly Disagree

2. Moderately disagree

3. Slightly disagree

4. Slightly agree

5. Moderately agree

6. Strongly agree

*Medtronic Business Restricted*

**CONFIDENTIAL**

056-F275 Rev G Clinical Investigation Plan Template

6. My abdominal wall interferes when I dress myself, take showers and cook
	
 
1. Strongly Disagree
 
2. Moderately disagree
 
3. Slightly disagree
 
4. Slightly agree
 
5. Moderately agree
 
6. Strongly agree
 

7. My abdominal wall interferes with my sexual activity
	
 
1. Strongly Disagree
 
2. Moderately disagree
 
3. Slightly disagree
 
4. Slightly agree
 
5. Moderately agree
 
6. Strongly agree
 

8. I often stay home because of my abdominal wall
	
 
1. Strongly Disagree
 
2. Moderately disagree
 
3. Slightly disagree
 
4. Slightly agree
 
5. Moderately agree
 
6. Strongly agree
 

9. I accomplish less at home because of my abdominal wall
	
 
1. Strongly Disagree
 
2. Moderately disagree
 
3. Slightly disagree
 
4. Slightly agree
 
5. Moderately agree
 
6. Strongly agree
 

*Medtronic Business Restricted*

**CONFIDENTIAL**

056-F275 Rev G Clinical Investigation Plan Template

10. I accomplish less at work because of my abdominal wall	

1. Strongly Disagree

2. Moderately disagree

3. Slightly disagree

4. Slightly agree

5. Moderately agree

6. Strongly agree

11. My abdominal wall affects how I feel everyday	

1. Strongly Disagree

2. Moderately disagree

3. Slightly disagree

4. Slightly agree

5. Moderately agree

6. Strongly agree

12. I often feel blue because of my abdominal wall	

1. Strongly Disagree

2. Moderately disagree

3. Slightly disagree

4. Slightly agree

5. Moderately agree

6. Strongly agree

## 19 Version History

Version	Summary of changes	Author(s)/Title
1.0	
 
Not Applicable, New Document
 
	
2.0	
 
Added 3-Month, 1-Year and 2-Year Follow-up visits throughout the protocol. Added secondary endpoints for long term follow-up timepoints.
 
Added clarification for mesh selection.
 
	
3.0	
 
Redefined Primary Safety Endpoint
 
Redefined Secondary Endpoints
 
Updated Ancillary Endpoints
 
Increased sample size from 120 to 192 and number of sites from 6 to up to 10
 
Added definitions for Readmission, Recurrence, Reoperation, SSE, SSI, and SSO
 
Updated Inclusion Criteria to specify type of hernia repair
 
Updated Exclusion Criteria to restrict hernia defect location
 
Removed AE relatedness assessment for underlying condition or disease
 
Added Figure 2 for clarity on classification of hernias
 
Increased window of visit schedule for all study visits
 
Updated Statical Design and Performance Goals
 
Added Clinical Study Design Justification Section 6.2.2
 
Added clarity on mesh usage and assessing hernia recurrence
 
Added Section 17.8 – Statement of Generalizability to Medicare Beneficiaries
 
Checked for applicability of CIP Template Version F
 
Terms aligned within document
 
	
4.0	
 
Added Appendix 18.11 for the Touch Surgery™ Ecosystem (TSE Sub-Study)
 
	
5.0	
 
Added “IRB” and “OR” to glossary list
 
Added the word “clinical” as clarification and consistency when referring to hernia recurrence in section 5.2.2, Secondary Endpoints
 
Removed duplicative wording in section 10.1.6, Post-Operative Follow-Up Visit
 
Added clarification on the target number of days for each follow-up assessment for Table 7 in section 10.2, Data Collection
 
	

*Medtronic Business Restricted*

**CONFIDENTIAL**

056-F275 Rev G Clinical Investigation Plan Template

# Enable Hernia Repair Clinical Investigation Plan

MDT21022

Version 5.0

Page 111 of 116

Medtronic

- Added “safety” as reference to endpoint for clarification in section 10.7, Assessment of Safety
- Updated Lost to Follow Up Section 10.10.3 to allow for patient lost to follow-up designation for 1-year visit and onward.
- Updated Sections 12.1 (Adverse Events) and 13.1 (Clinical Events Committee Review) to specify CEC adjudication of SAEs, deaths and SSEs through primary endpoint analysis (30 days post-procedure) instead of through study participation.
- Updated section 12.5.2 for adverse event and device deficiency reporting timeframes and updated section 12.6 (Subject Death) to cross reference
- Updated Section 14 to follow clarifications made in the pre-specified Statistical Analysis Plan (SAP). The SAP was completed prior to any analyses of the study objectives.
  - Clopper Pearson method vs exact binomial test.
  - Use of 30 calendar days for assessments “through 30 days”.
  - Corrections of previously incorrect information (alignment with Medtronic Standard Operating Procedures, use of 0.05 two-side alpha was never used in the study, etc.).
- Corrected section number for clinicaltrials.gov reference in section 15.1
- Removed Optional Touch Surgery Ecosystem (TSE Sub Study) section 18.11. This sub-study was not incorporated at the investigational centers and removed in this version of the CIP.

*Medtronic Business Restricted*

**CONFIDENTIAL**

056-F275 Rev G Clinical Investigation Plan Template

2.0	
Update referenced CIP version since CIP V4.0 was not implementedAdditional clarification on how subjects will be chosen for objectives defined for “through 30 days”Clarification that, when available, CEC adjudication will be used for all analyses	
3.0	
Update following CIP V5.0
CEC adjudication requirementsRemoved changes as compared to CIP V3.0Site recruitment limits	

2. List of Abbreviations and Definitions of Terms

Abbreviation	Definition
ACHQC	Abdominal Core Health Quality Collaborative
ADE	Adverse Device Effect
AE	Adverse Event
CDC	Centers for Disease Control and Prevention
CI	Confidence Interval
CIP	Clinical Investigational Plan
CSR	Clinical Study Report
DD	Device Deficiency
FAS	Full Analysis Set
FDA	Food and Drug Administration
MedDRA	Medical Dictionary for Regulatory Activities
PD	Protocol Deviation
PG	Performance Goal
PPAS	Per Protocol Analysis Set
RAS	Robotic Assisted Surgery
SADE	Serious Adverse Device Effect
SAE	Serious Adverse Event
SAP	Statistical Analysis Plan
SOC	System Organ Class
SSE	Surgical-Site Event
SSI	Surgical-Site Infection
SSO	Surgical-Site Occurrence
UADE	Unanticipated Adverse Device Effect
US or USA	United States of America

3. Introduction

A hernia is a protrusion of tissue or part of an organ through bone, muscular tissue, or membrane. Inguinal hernias occur in or near the inguinal canal and ventral hernias occur in the abdomen wall. Lifetime risk for inguinal hernia occurrence is 3% for women and 27% for men. Ventral hernias occur in the abdomen wall and are sometimes referred to as abdominal hernias; sub-types of ventral hernias include incisional hernias, umbilical hernias, and epigastric hernias. The traditional treatments for hernia are open and laparoscopic surgeries. In recent years, Robotic assisted surgery emerged and has gradually been adopted as an alternative. The Medtronic Hugo™ RAS system is a modular robotic platform for performing robotic assisted minimally invasive surgery. This clinical study is designed to evaluate the safety and effectiveness of the Hugo™ RAS system for subjects in inguinal and ventral hernia repair surgery.

This statistical analysis plan (SAP) serves as a guideline for study Biostatistician(s), Statistical Programmer(s), and other stakeholders for internal use. The purpose is to provide general, and in some instances, specific guidelines from which the analysis will proceed. It was created in accordance with the clinical investigational plan (CIP) version 5.0, dated 02-Sep-2025. If the CIP is updated, this SAP will be updated if the SAP content is impacted.

Changes to the plan may become necessary as the study progresses or when the CIP needs to be updated or as other unexpected events emerge. The planned analyses identified in this document may be included in regulatory submissions and/or future manuscripts. They will also be the basis of the Primary Endpoint (30-Day) Clinical Study Report (CSR) for this study. Any post-hoc analyses, unplanned analyses, or changes to planned analyses will be clearly identified in the CSR.

4. Study Objectives

4.1 Primary Objectives

The primary objectives of this study are to demonstrate that the Medtronic Hugo™ RAS system is safe and effective when used for inguinal and ventral robotic hernia repair.

4.1.1 Primary Objective #1 (Effectiveness) Endpoint

The primary effectiveness endpoint is the surgical success rate defined as the procedure not going into conversion. Conversion is defined as the switch from the robotic-assisted approach using the Hugo™ RAS system to laparoscopic, open surgery, or use of an alternative robotic-assisted system. Procedural steps that are usually performed without robotic assistance per standard of care, including but not limited to mesh insertion, suture needle removal, or tacking, are not considered a conversion and will not contribute to the primary effectiveness endpoint.

4.1.2 Primary Objective #2 (Safety) Endpoint

The primary safety endpoint is the overall rate of subjects with one or more study procedure- and/or device-related surgical-site events (SSEs), from the first incision of the hernia repair procedure through 30 days post-procedure. SSE is defined as the following complications:

- Surgical-site occurrence (SSO):
 - Bleeding, Hemorrhage: Requiring transfusion
 - Bowel Injury
 - Bowel Obstruction
 - Note: Functional obstruction associated with general anesthesia and/or pain killer drugs (opioids) is excluded for this endpoint
 - Cellulitis
 - Epigastric Vessel Injury
 - Symptomatic Hematoma: Requiring procedural intervention
 - Symptomatic Seroma: Requiring procedural intervention
 - Symptomatic Edema: Requiring procedural intervention

- Note: Procedural intervention is defined as percutaneous drainage, wound opening or debridement, suture excision, or mesh removal (partial or total)
- Surgical-site infection (SSI): Infection occurring where the surgery took place, including superficial, deep, and organ space infections (standardized definition developed by the CDC)

The relatedness of the SSEs being classified as “procedure- and/or device-related” may include three scenarios, all of which are included in this primary objective: (1) only procedure-related SSEs, (2) only device-related SSEs, and (3) SSEs that are both procedure- and device-related. In this study, procedure-relatedness refers to an AE that occurs due to the hernia repair procedure with the Hugo™ RAS system, and device-relatedness refers to an AE that results from the presence or performance (intended or otherwise) of the Hugo™ RAS system.

4.2 Secondary Objectives

The secondary objective of this study is to demonstrate that the Medtronic Hugo™ RAS system performs as intended when used in inguinal and ventral hernia repair robotic assisted surgery. The secondary endpoints of this study will assess the overall performance of the Medtronic Hugo™ RAS system when used for hernia repair.

4.2.1 Secondary Objective Endpoints

Secondary objectives include descriptive analyses of secondary endpoints. The following safety and performance endpoints will be summarized for the period through 30 days post-procedure (defined as 30 calendar days after the procedure) to assess the overall safety and performance of the Medtronic Hugo™ RAS system when used for hernia repair robotic assisted surgery:

- Complication rate: Overall rate of subjects with one or more procedure- and/or device-related complications (Clavien-Dindo Grade I or higher), from the first incision through 30 days post-procedure
- Major complication rate: Overall rate of subjects with one or more major procedure- and/or device-related complications (major defined here as Clavien-Dindo Grade III or higher), from the first incision through 30-days post-procedure
- Operative time: time from skin incision to skin closure
- Readmission rate through 30 days post-procedure: Admission for a direct consequence or complication associated with the treated hernia or with the surgical procedure to treat the hernia
- Reoperation rate through 30 days post-procedure: Operation for a direct consequence or complication associated with the treated hernia or with the surgical procedure to treat the hernia
- Recurrence rate through 30 days post-procedure: Clinical hernia recurrence is defined as a palpable fascial defect and/or a clinically manifested bulge within 7 cm of the original repair, exacerbated by a Valsalva maneuver during physical examination by a study investigator.

The following long-term secondary endpoint will be assessed through 2 years post-procedure in all treated subjects:

- Recurrence rate through 2 years post-procedure

Note: Suspected hernia recurrence(s) reported by a subject, but not confirmed by an investigator, will not be considered as a clinical hernia recurrence for this endpoint, but will be reported separately as a subject-reported recurrence in the final report.

Clinical hernia recurrence is defined as a palpable fascial defect and/or a clinically manifested bulge within 7 cm of the original repair, exacerbated by a Valsalva maneuver during physical examination by a study investigator.

4.3 Ancillary Objectives

Descriptive analyses of other pre-specified outcome measures beyond the primary and secondary objectives will be exploratory in nature and are not intended as a focus of the study for the evaluation of the study device.

The following data will be collected as applicable:

- Estimated intraoperative blood loss
- Transfusion rate through 30 days
- Hospital length of stay
- Mortality through 30 days
- Device- and/or procedure-related AEs through 2 years
- Readmission rate through 2 years: Admission for a direct consequence or complication associated with the treated hernia or with the surgical procedure to treat the hernia
- Reoperation rate through 2 years: Operation for a direct consequence or complication associated with the treated hernia or with the surgical procedure to treat the hernia
- Surgeon experience
- Pain scores at baseline, 30-days, and 3-months (Abdominal Core Health Quality Collaborative [ACHQC] questionnaire)

5. Investigation Plan

This study is a prospective, multicenter, single-arm pivotal study that will enroll 192 subjects with either an inguinal or ventral robotic hernia repair procedure using the Medtronic Hugo™ RAS system. Subjects will be followed up to two years from the index hernia repair procedure. This study will be conducted in the United States (US) with up to ten study sites. The study required procedures and follow-up consist of the following: Screening, Surgical Procedure, Hospital Discharge, and Post-Discharge Follow-Up at 30 days (± 7 days), 3 months (± 14 days), 1 year (± 30 days) and 2 years (± 30 days).

For the study to be successful, it must meet the primary effectiveness objective, which is based on combined cohorts of inguinal and ventral. The primary safety objective must be met for each corresponding hernia cohort (inguinal, ventral) independently. That is to say, the primary safety objective could be successful for one hernia cohort and failed for the other.

6. Determination of Sample Size

The sample size for the study was estimated based on the primary safety and effectiveness hypotheses.

The effectiveness hypothesis is to test if the surgical success rate is above the performance goal. The sample size for primary effectiveness is based on combined cohorts of inguinal and ventral. A performance goal of 85% (100%-conversion rate) is pre-defined to test the statistical hypothesis. Assuming a success rate of 93%, a sample size of 172 subjects for the combined inguinal and ventral hernia cohort will provide 90% of power with one-sided alpha of 0.025. Calculation was performed using the PASS 2023. Accounting for 10% attrition rate, the enrollment is 192 subjects with a hernia repair procedure.

The primary safety objective is also part of the consideration for the sample size determination. The primary safety endpoint is the rate of subjects with any procedure- and/or device-related SSEs from the first incision through 30 days post-procedure. The primary safety objective, assessed separately for each hernia cohort, is based on a performance goal of 30% and expected safety event rate of 15% for the cohort. A sample size of 86 will provide 86% power with a one-sided alpha of 0.0125 (Bonferroni Correction for hernia cohort). Calculation was performed using the PASS 2023. Accounting for 10% attrition rate, the enrollment is 96 per cohort or 192 total subjects with a hernia repair procedure.

An attrition rate of 10% was assumed to ensure an adequate sample for each objective, resulting in 192 total subjects (96 per hernia cohort).

Endpoint	Performance Goal	Expected Study Rate	Minimum Sample Size	Minimum Power	Minimum Alpha
Primary Effectiveness	85%	93%	172	90%	0.025
Primary Safety	30%	15%	86	86%	0.0125

The secondary objectives will be assessed using descriptive statistics and no sample size assessment was made for these objectives.

7. Statistical Methods

7.1 Study Subjects

7.1.1 Disposition of Subjects

Subject disposition will be illustrated in a CONSORT diagram. The number of subjects screened, treated, discontinued during the study, as well as the reasons for discontinuations will be summarized for all centers combined and each center separately. Reason for study discontinuation will also be provided as a by-subject listing.

7.1.2 Clinical Investigation Plan (CIP) Deviations

The number protocol deviations will be reported by deviation type.

7.1.3 Analysis Sets

The following populations will be considered for the analysis of data for this study. All enrolled subjects will be included in a subject disposition table indicating reasons for exclusion from each analysis set.

Enrolled Analysis Set

All subjects who signed informed consent.

Full Analysis Set

The full analysis set (FAS) is defined as all enrolled subjects in whom the Hugo™ RAS procedure is begun, defined as the first skin incision. If a subject is consented, but the first incision does not occur (e.g., if the subject becomes ineligible during the timeframe between consent and the procedure day), the subject will not be considered part of the FAS. The FAS will be the primary analysis set for the evaluation of the primary, secondary, and ancillary endpoints. In the case of missing data with no imputation, some subjects may be excluded from an objective analysis using the FAS analysis set. Consider imputation plans defined in section 7.4.

Per Protocol Analysis Set

The per protocol analysis set (PPAS) is a subset of the FAS including only those subjects without any major protocol deviations. Major deviation reasons include “Enrolled subject did not meet enrollment criteria” and “Unauthorized use of investigational device.” Reasons for exclusion of subjects from PPAS will be documented in the CSR.

7.1.4 Assessment of Treated Hernia Type

Subjects enrolled in the study are indicated for inguinal (unilateral or bilateral) or ventral hernia (with a maximum size of <10cm). In some cases, subjects may have hernia treated in a way that is adjacent or beyond the expected items above. For example, an inguinal subject may have an unknown femoral hernia near the intended inguinal hernia; in this case, the surgeon might consider it most ethical to fix both hernia with Hugo during the single procedure. In another example, a surgeon may identify ventral hernia that require repair after starting the inguinal procedure.

For the purposes of analysis, subjects will be included with the initially intended hernia type (expected to be inguinal in most cases where multiple hernia types are treated). The main safety analyses will include all events for the subjects with the initially intended hernia type. For cases where a subject has both inguinal and ventral hernia, adverse events will be assessed to determine whether any events are related primarily to the ventral hernia; in these cases, a sensitivity analysis may be added for the primary safety objective to include this event/subject in the ventral cohort in addition to the inguinal cohort.

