7.9.2.2 Endpoint Definition and Derivation

The rate of SSE within 30 days is calculated as the proportion of subjects who experience an SSE during the procedure and through 30 days after the procedure. SSE are defined in detail in section 4.1.2. The AE start date of the adverse event will be used to determine when an SSE was experienced.

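### The optional dual-hernia sensitivity analysis in SAP 7.1.4 adds subjects to the ventral cohort only if they had a ventral-related event, which biases the ventral SSE rate upward, against the device

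*SAP*

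**What the plan says.** SAP 7.1.4 foresees that a surgeon may find and repair a second hernia type during the index procedure. For analysis, "subjects will be included with the initially intended hernia type", which the SAP expects to be inguinal in most of these cases. On safety it says: "The main safety analyses will include all events for the subjects with the initially intended hernia type".

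Subjects with both types get an extra screening step, worded as "adverse events will be assessed to determine whether any events are related primarily to the ventral hernia; in these cases". What follows from it is permissive: the SAP says that "a sensitivity analysis may be added for the primary safety objective". The stated purpose of that analysis is "to include this event/subject in the ventral cohort in addition to the inguinal cohort". The analysis is therefore optional and follows the finding of an event. It keeps the subject in the inguinal cohort as well.

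SAP 7.9.2.2 defines the endpoint as a proportion of subjects: "The rate of SSE within 30 days is calculated as the proportion of subjects who experience an SSE during the procedure and through 30 days". Nothing in SAP 7.1.4, 7.4 or 7.9.2 brings into the ventral denominator a dual-hernia subject whose ventral hernia was repaired without a ventral-related event.

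**The concern.** In a proportion, the numerator and denominator should come from the same group, and that group should be defined without reference to the outcome. Here the event itself is the entry criterion. Subjects with a ventral repair and a ventral SSE are added to both counts, while subjects with a ventral repair and no event are added to neither. Those who enter because of an SSE have a 100% event rate by construction.

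The direction of the result is then fixed in advance. An analysis that can only raise the ventral rate says little about whether the ventral finding is robust to how dual-hernia subjects are classified. SAP section 5 lets the safety objective succeed in one cohort and fail in the other, so a ventral sensitivity result close to the limit would attract attention. A sound result could look fragile for arithmetic reasons alone.

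**Working it through.** **Inputs.** SAP section 6 gives the design figures: the safety objective "is based on a performance goal of 30% and expected safety event rate of 15% for the cohort", with 86 evaluable subjects per cohort, one-sided alpha 0.0125 and 86% power. The test is an exact binomial test (protocol 14.4.2; SAP 7.9.2.5). The number of dual-hernia subjects assigned to the inguinal cohort but with a ventral repair, m, is not in the documents; I assume 2 to 20.

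**The plan's own figure.** The largest c with P(X ≤ c | 86, 0.30) ≤ 0.0125 is c = 16, with actual alpha 0.01175. Power is P(X ≤ 16 | 86, 0.15) = 0.8607, so the stated 86% reproduces. At 0.025 the limit is 17 events: P(X ≤ 17 | 86, 0.30) = 0.0223.

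**The two rules.** Let X be the SSE subjects among the 86 ventral subjects, and Y the SSE subjects among the m dual-hernia subjects, all with the same true rate p. Assume every dual-hernia SSE is attributed to the ventral repair and that only SSEs trigger entry.

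- As written: (X + Y)/(86 + Y)
- All dual-hernia subjects: (X + Y)/(86 + m), with expectation p

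Adding one event subject to X/n changes the rate by (X + 1)/(n + 1) − X/n = (1 − X/n)/(n + 1), which is positive whenever X < n. From 17/86 this is (1 − 0.1977)/87 = 0.0092, or 0.92 points.

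**Expected bias.** Under the rule as written, the expected rate is Σ P(Y = y) × (86p + y)/(86 + y), with Y binomial(m, p). As a check for p = 0.15 and m = 5, putting in the mean Y = 0.75 gives (12.9 + 0.75)/86.75 = 15.73%, which agrees with the full sum. At p = 15%:

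| m (assumed) | Expected rate as written | Bias (points) | P(p-value ≤ 0.025), as written | P(p-value ≤ 0.025), all dual added |
|---|---|---|---|---|
| 2 | 15.29% | +0.29 | 89.7% | 89.7% |
| 5 | 15.73% | +0.73 | 87.0% | 91.9% |
| 10 | 16.44% | +1.44 | 82.0% | 92.3% |
| 20 | 17.84% | +2.84 | 71.8% | 95.9% |

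At 4.5%, the literature rate for ventral repair in SAP 7.9.2.4, the bias is +0.1 points (m = 2) to +1.0 (m = 20).

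**Direction.** At a true rate of 30%, the chance of passing at 0.025 is 2.23% with no dual-hernia subjects. Under the rule as written it is 1.02% with m = 5 and 0.48% with m = 10. Under these assumptions the rule makes a false pass less likely.

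**Near the boundary, one-sided 0.025.**

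| Main ventral result | Assumed dual-hernia subjects | As written | All dual added |
|---|---|---|---|
| 17/86, p = 0.0223 | 5, of whom 1 has a ventral SSE | 18/87 = 20.7%, p = 0.0344 | 18/91 = 19.8%, p = 0.0192 |
| 16/86, p = 0.0118 | 5, of whom 2 have a ventral SSE | 18/88 = 20.5%, p = 0.0298 | 18/91 = 19.8%, p = 0.0192 |
| 13/86, p = 0.0011 | 5, of whom 2 have a ventral SSE | 15/88 = 17.0%, p = 0.0040 | 15/91 = 16.5%, p = 0.0023 |

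The first two rows change the reading. The third, at about the planned 15% rate, does not.

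**The case against.** The strongest defence is that the SAP has a narrow purpose here. A ventral-related event may be booked under inguinal because of the intended-type rule, and adding it back asks whether the ventral conclusion survives. Read that way, it is a deliberate one-sided stress test. This stands in part: a conservative check is legitimate if it is labelled as one. SAP 7.1.4 does not label it so, and a reader will take the result as a ventral SSE rate.

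It is also true that the analysis is optional and that trial success rests on the main analysis by intended type. Both points stand and limit the importance of the matter.

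One could read the words introducing the analysis as covering all dual-hernia subjects. The singular reference to the event or subject points the other way; at the least the sentence is ambiguous. The trigger is also worded as adverse events, not SSEs. A subject with only a non-SSE ventral event could enter as event-free, so the 100% event rate holds only for SSE-triggered entries. Entry would still depend on the outcome.

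A last objection bears on the remedy. If every dual-hernia subject is added but only ventral-attributed SSEs are counted, a subject whose SSE is attributed to the inguinal repair enters as event-free and dilutes the rate. Attribution may also be uncertain when both repairs are done in one operation. This stands, and the fix allows for it.

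**Conclusion.** The point holds as a minor defect in an optional analysis. Selection on the outcome biases the ventral sensitivity rate upward, by about 0.3 to 1.4 points for 2 to 10 dual-hernia subjects at a true rate of 15%. This rests on an assumed count, on equal rates in dual-hernia and other ventral subjects, and on SSE-triggered entry with all their SSEs treated as ventral. At 0.025 it changes the reading only when the main result is on or close to the limit of 17/86.

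Three stronger readings are tempting and not supported:

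- **A passing ventral objective could be turned into a failure.** It could not. The main safety analysis is fixed by intended type, and the sensitivity analysis does not enter the success rule.
- **The result should be held to 0.0125.** On that view, 15/86 plus two ventral SSEs gives 17/88 (p = 0.0164) and fails. Protocol 14.12 applies no multiplicity adjustment to sensitivity analyses. Even under Holm in SAP 7.5, the larger of the two p-values is compared with 0.025 once the smaller has passed. So 17/88 would normally pass.
- **Subjects are moved from inguinal to ventral, lowering the inguinal rate.** They are counted in both cohorts, and the inguinal result does not change.

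**What to change.** Amend SAP 7.1.4 so that the sensitivity analysis is run whenever any dual-hernia subject exists, instead of at discretion after an event is seen. Add to the ventral cohort every dual-hernia subject whose ventral hernia was repaired at the index procedure and whose 30-day status is available under SAP 7.4, with or without an event. Keep them in the inguinal cohort too, as now.

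Count all their procedure- and/or device-related SSEs, consistent with the main analysis; this avoids the dilution described above. Alongside it, report a version counting only SSEs not clearly attributable to the inguinal repair.

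The cost is one or two sentences in the SAP, a small amount of extra programming, and an attribution decision for the second version. No new data are needed beyond the record of which hernias were repaired, which SAP 7.1.4 already presumes.
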